**Table 10. Possible Clinical Outcomes for Participants With or Without CIS at Randomization and EFS Evaluation**

Population	Disease Assessment	EFS Event Y/N
Participants with CIS at randomization	Progressive disease [a] before achieving a CR for participants with CIS only at randomization	Y
	Progressive disease after achieving a CR	Y
	Recurrence of high-grade disease before achieving a CR for participants with CS and concurrent papillary disease at randomization	Y
	Recurrence of high-grade disease after achieving a CR	Y
	Persistence of CIS (non-CR) [b]	Y
	Recurrence of low-grade disease	N
Participants without CIS at randomization	Progressive disease	Y
	Recurrence of high-grade disease	Y
	Recurrence of low-grade disease	N

[a] Including appearance of new high-grade Ta or T1 disease for participants with CIS only at randomization.

[b] Persistence of CIS after induction, with CR after re-induction is not considered an event.

**Table 11. Outcome and Event Dates for the Primary Analysis of EFS-Cohort A**

Scenario	Date of event/censoring	Outcome
No adequate baseline assessment	Date of randomization [a]	Censored [a]
Event - After at most one missing or inadequate post-baseline disease assessment, OR - $\leq 24$ weeks after the date of randomization	Date of event	Event
Event - After 2 or more missing or inadequate post-baseline disease assessments	Date of last adequate disease assessment documenting no event	Censored
No event	Date of last adequate disease assessment documenting no event	Censored

[a] However, if the participant dies  $\leq 24$  weeks after the date of randomization the death is an event with date on death date

The primary efficacy analysis will compare the EFS time based on the investigator assessment between Arm A and Arm C and will be performed using a 1-sided stratified log-rank test as described in [Section 5.1](#). The following analyses will be based on the FAS.

The treatment effect will be estimated using a Cox's Proportional Hazard model stratified by the randomization strata to calculate the hazard ratio along with 95% CIs. Each stratum will define a separate baseline hazard function (using the 'STRATA' statement in SAS PROC PHREG), ie for the i-th stratum the hazard function is expressed as:  $h(i;t) = h(i,0;t) \exp(x\beta)$ ,

where  $h(i,0;t)$  defines the baseline hazard function for the  $i$ -th stratum and  $x$  defines the treatment arm (0=control arm, 1= experimental arm) and  $\beta$  is the unknown regression parameter.

Ties will be handled using the Exact option in SAS (Ties=Exact option in SAS PROC PHREG).

Kaplan-Meier estimates (product-limit estimates) will be presented by treatment arm together with a summary of associated statistics including the median EFS time with 2-sided 95% CIs. In particular, the EFS rate at 6, 12, 18, 24, 30, 36, 42, and 48 months will be estimated with corresponding 2-sided 95% CIs. The CIs for the median will be calculated according to Brookmeyer and Crowley (1982) and the CIs for the survival function estimates at the time points defined above will be derived using the log-log transformation according to Kalbfleisch and Prentice (2002) (conftype=loglog default option in SAS Proc LIFETEST) with back transformation to a CI on the untransformed scale. The estimate of the standard error will be computed using Greenwood's formula. A Kaplan-Meier plot for EFS will be generated.

Frequency (number and percentage) of participants with each event type (progression of disease, recurrence of high-grade disease, persistence of CIS, or death) and censoring reasons will be presented by treatment arm. Reasons for censoring will be summarized according to the categories in Table 12 following the hierarchy shown.

**Table 12. EFS Censoring Reasons and Hierarchy – Cohort A**

Hierarchy	Condition	Censoring Reason
1	No adequate baseline assessment	No adequate baseline assessment[a]
2	Event after 2 or more missing or inadequate post-baseline disease assessments	Event after 2 or more missing assessments
3	No event and [withdrawal of consent date $\geq$ date of randomization]	Withdrawal of consent
4	No event and lost to follow-up in any disposition page	Lost-to-follow-up
5	No event and [EOS][b] present OR all EOT disposition pages of all drugs in the treatment arm say participant will not continue into any subsequent phase of the study] and no adequate post-baseline disease assessment	No adequate post-baseline disease assessment
6	No event and none of the conditions in the prior hierarchy are met	Ongoing without an event

[a] However, if the participant dies  $\leq$ 24 weeks after the date of randomization the death is an event with date on death date

[b] EOS here refers to completion of follow-up disposition page.

For the participants with a PD event for EFS as assessed by the investigator, the number and percentage of participants with the following types of PD (defined hierarchically) will be presented:

- Progression to metastatic disease (defined as N+, M+)
- Progression to muscle invasive disease (defined as  $\geq$  T2 disease)
- Stage Progression (defined as high-grade Ta or T1 disease)

The EFS time or censoring time and the reasons for censoring will also be presented in a participant listing.

### **Time of Follow-Up for EFS**

A Kaplan-Meier plot for EFS follow-up duration will also be generated to assess the follow-up time in the treatment arms reversing the EFS censoring and event indicators.

#### **6.1.2. Complete response as assessed by BICR (Cohort B1 only)**

##### **6.1.2.1. Primary analysis**

In this study, disease may be assessed through cytology, cystoscopy, biopsy, and imaging scans. Cytology, cystoscopy, and biopsy (as clinically indicated) will be required every 12 weeks for 2 years following date of first dose (after cycle 10 assessments will occur at cycle 14 and 16 followed by every 12 weeks) until first occurrence of progression of disease, recurrence of high-grade disease, or persistence of CIS (for participants with CIS at baseline) regardless of initiation of subsequent anti-cancer therapy. In addition, disease status will be assessed through imaging in the case of a positive cytology or cystoscopy and at screening, every 24 weeks for 2 years after initiation of study intervention until first occurrence of progression of disease, recurrence of high-grade disease, persistence of CIS (for participants with CIS at baseline) regardless of initiation of subsequent anti-cancer therapy, or EOT.

Complete Response (CR) is defined as histologic disappearance of malignancy on bladder biopsy with negative cytology and cystoscopy or negative cytology and positive cystoscopy with biopsy-proven low-grade Ta lesion or nonmalignant tissue at the 12-week assessment for participants with CIS at baseline by the BICR. CR will also be assessed by investigator.

A listing for CR will be provided.

#### **6.1.3. Event-free survival as assessed by investigator (Cohort B2 only)**

##### **6.1.3.1. Primary analysis**

In Cohort B2, disease may be assessed through cytology, cystoscopy, biopsy, and imaging scans. Cytology and cystoscopy are to be conducted at screening, every 12 weeks for 2 years following initiation of study intervention until first occurrence of progression of disease, recurrence of high-grade disease, regardless of initiation of subsequent anti-cancer therapy. Biopsies and imaging are performed at screening and as clinically indicated.

EFS is defined as the time from initiation of study intervention until recurrence of high-grade disease, progression of disease, or death due to any cause, whichever occurs first.

An event is as defined in Table 13. The censoring and event date options to be considered for the EFS analysis are presented in Table 14.

**Table 13. Possible Clinical Outcomes for Participants Without CIS at baseline and EFS Evaluation**

Population	Disease Assessment	EFS Event Y/N
Participants without CIS at baseline	Progressive disease	Y
	Recurrence of high-grade disease	Y
	Recurrence of low-grade disease	N

**Table 14. Outcome and Event Dates for the Primary Analysis of EFS – Cohorts B1 and B2**

Scenario	Date of event/censoring	Outcome
No adequate baseline assessment	Date of initiation of study intervention [a]	Censored [a]
Event - After at most one missing or inadequate post-baseline disease assessment, OR - $\leq$ 24 weeks after the date of first dose	Date of event	Event
Event - After 2 or more missing or inadequate post-baseline disease assessments	Date of last adequate disease assessment documenting no event	Censored
No event	Date of last adequate disease assessment documenting no event	Censored

[a] However, if the participant dies  $\leq$  24 weeks after the date of first dose the death is an event with date on death date

EFS (months) = [date of event or censoring – date of first dose + 1] / 30.4375

**Table 15. EFS Censoring Reasons and Hierarchy – Cohorts B1 and B2**

Hierarchy	Condition	Censoring Reason
1	No adequate baseline assessment	No adequate baseline assessment [a]
2	Event after 2 or more missing or inadequate post-baseline disease assessments	Event after 2 or more missing assessments
3	No event and [withdrawal of consent date $\geq$ date of first dose]	Withdrawal of consent
4	No event and lost to follow-up in any disposition page	Lost-to-follow-up
5	No event and [EOS][b] present OR all EOT disposition pages of all drugs in Cohort B2 say participant will not continue into any subsequent phase of the study] and no adequate post-baseline disease assessment	No adequate post-baseline disease assessment

**Table 15. EFS Censoring Reasons and Hierarchy – Cohorts B1 and B2**

Hierarchy	Condition	Censoring Reason
6	No event and none of the conditions in the prior hierarchy are met	Ongoing without an event

[a] However, if the participant dies  $\leq 24$  weeks after the date of first dose the death is an event with date on death date

[b] EOS here refers to completion of follow-up disposition page.

A listing for EFS will be provided.

## 6.2. Secondary Endpoint(s)

### 6.2.1. Safety endpoints

Refer to [Section 6.6](#).

### 6.2.2. Efficacy endpoints

The following analyses will be based on the FAS by treatment arm for Cohort A and for Cohorts B1 and B2, unless otherwise specified. Summaries will only be provided for Cohort A. For Cohorts B1 and B2, listings will be provided for efficacy endpoints as indicated.

For Cohort A, disease endpoints (CR, DoCR, time to recurrence of low-grade disease, and DSS) will be analyzed based on investigator assessment. EFS by BICR assessment will be analyzed as a secondary endpoint using the same methodology that is described in [Section 6.1.1.1](#) now referring to BICR assessment instead of investigator assessment.

#### 6.2.2.1. Event-free survival as assessed by the investigator (for Arm B vs Arm C in Cohort A)

Refer to [Section 2.2.2](#) the key secondary estimand (EFS for Arm B vs Arm C).

The primary analysis of the key secondary endpoint of EFS for Arm B vs Arm C will repeat the primary analysis of the primary endpoint of EFS for Arm A vs Arm C (p-value, HR and 95% CIs) described in [Section 6.1.1.1](#).

#### 6.2.2.2. Overall survival (Cohort A only)

Overall survival (OS) is a key secondary endpoint for Cohort A.

The following analyses will be based on the FAS.

OS is defined as the time from the date of randomization to the date of death due to any cause. Participants last known to be alive will be censored at date of last contact.

$$\text{OS (months)} = [\text{date of death or censoring} - \text{date of randomization} + 1]/30.4375$$

The primary analysis of OS will compare the OS time between each of the experimental arms and the control arm and will be performed using a 1-sided stratified log-rank test as described in [Section 5.1](#).

The treatment effect will be estimated using a Cox's Proportional Hazard model stratified by the randomization strata to calculate the hazard ratio. Each stratum will define a separate baseline hazard function (using the 'STRATA' statement in SAS PROC PHREG), ie for the  $i$ -th stratum the hazard function is expressed as:  $h(i;t) = h(i,0;t) \exp(x\beta)$ , where  $h(i,0;t)$  defines the baseline hazard function for the  $i$ -th stratum and  $x$  defines the treatment arm (0=control arm, 1= experimental arm) and  $\beta$  is the unknown regression parameter.

Ties will be handled using the Exact option in SAS (Ties=Exact option in SAS PROC PHREG).

In order to account for the group sequential design in this study, the repeated CI (RCI) method (Jennison and Turnbull, 2000), will be used to construct the 2-sided RCIs for the hazard ratio at the interim and the final analyses of OS.

In addition, the unadjusted 95% CIs for the hazard ratio will also be reported at the interim and the final analyses for OS.

Kaplan-Meier estimates (product-limit estimates) will be presented by treatment arm for Cohort A along with a summary of associated statistics including the median OS time with 2-sided 95% CIs. In particular, the OS rate at 12, 24, 36, 48, 60, 72, and 84 months will be estimated with corresponding 2-sided 95% CIs. The CIs for the median will be calculated according to Brookmeyer and Crowley (1982) and the CIs for the survival function estimates at the time points defined above will be derived using the log-log transformation according to Kalbfleisch and Prentice (2002) (conftype=loglog default option in SAS Proc LIFETEST) with back transformation to a CI on the untransformed scale. The estimate of the standard error will be computed using Greenwood's formula. A Kaplan-Meier plot for OS will be generated.

Frequency (number and percentage) of participants with an event (death) and censoring reasons will be presented by treatment arm.

Reasons for censoring will be summarized according to the categories in Table 16 following the hierarchy shown.

**Table 16. OS Censoring Reasons and Hierarchy**

Hierarchy	Condition	Censoring Reason
1	No event and [withdrawal of consent date $\geq$ 'start date']	Withdrawal of consent
2	No event and [lost to follow-up in any disposition page OR (data cut-off date – last contact date > 365 days)]	Lost to follow-up
3	No event and none of the conditions in the prior hierarchy are met	Alive

The OS time or censoring time and the reasons for censoring will also be presented in a participant listing.

### Time of Follow-Up for OS

A Kaplan-Meier plot for OS follow-up duration will also be generated to assess the follow-up time in the treatment arms reversing the OS censoring and event indicators.

#### 6.2.2.3. Sensitivity analyses for event-free survival (Cohort A only)

The following analyses will be performed to explore the robustness of the primary analysis results. The sensitivity analyses will repeat the primary analysis (p-value, HR and 95% CIs) described in [Section 6.1.1.1](#) with the modifications below:

- EFS based on BICR results following the definitions in Table 10 and the censoring rules outlined in Table 11 and Table 12.
- EFS based on investigator assessment where the date of the event for participants with persistence of CIS is the date of randomization (refer to Supportive Estimand 1 [Section 2.2.3](#))
- EFS based on investigator assessment following the definitions in Table 10 and the censoring rules outlined in Table 11 and Table 12 for participants in the per-protocol analysis set (refer to Supportive Estimand 2 [Section 2.2.3](#))
- EFS based on investigator assessment following the definitions in Table 10 and the censoring rules outlined in Table 11 and Table 12 and using an unstratified analysis.
- EFS based on investigator assessment following the definitions in Table 10 and modifying the censoring rules in Table 11 (update footnote “a” to “If the participant dies  $\leq 24$  weeks after the date of randomization and did not initiate new anti-cancer therapy, the death is an event with date on death date”) and Table 12 to include initiation of subsequent anti-cancer therapies as a censoring reason after “no adequate baseline assessment”.
- EFS based on investigator assessment following the definitions in Table 10 and the censoring rules outlined in Table 11 and Table 12 and using CIS stratification factor derived based on the data entered by the investigator in the “Oncology Biopsy” eCRF at Screening.
- EFS based on investigator assessment following the definitions in Table 10 and modifying the censoring rules in Table 11 and Table 12 to not censor events after 2 or more missing or inadequate post-baseline disease assessments (ie. all events will be counted).
- If  $>10\%$  of deaths are due to COVID-19, an analysis will be performed for EFS (primary definition excluding COVID-19 related deaths) by treating COVID-19 related deaths as a competing risk event.
- If there are  $>10\%$  of participants with missed visits resulting in 2 or more missing assessments or inadequate post-baseline disease assessments due to COVID-19 before EFS events, censoring for event after 2 or more missing or inadequate disease assessment

will not occur per Table 11 and Table 12 and the EFS event will be counted (i.e. not censored per Table 11 and Table 12).

### **Sensitivity analysis for possibly informative censoring**

To assess impact of possibly informative censoring due to potentially imbalanced dropouts on the primary analysis of EFS by the investigator, a reference-based multiple imputation method based on Bayes Gibbs sampling as outlined by Lu, Li, and Koch (2015) will be implemented if imbalanced dropouts are observed between treatment arms. Imputations will be performed for participants who were censored due to lost to follow-up, withdrawal of consent, or no adequate post-baseline disease assessment as described in Table 12. This method assumes that the hazard for the participants in Arm A (or Arm B) who are censored due to the above censoring reasons lies between the hazard for the participants in Arm A (or Arm B) who continued and the hazard for the participants in Arm C, while the hazard for the participants in Arm C who are censored due to the above censoring reasons is the same as the hazard for the participants in Arm C who continued. Other sensitivity analysis methods for possibly informative censoring may also be considered, as applicable, and as appropriate.

### **Methods for evaluating the validity of model assumptions**

The proportional hazards assumption will be checked visually by plotting log(-log(EFS)) versus log(time) within each randomization stratum.

Schoenfeld residuals for the stratified Cox's proportional regression model will be plotted to investigate graphically violations from the proportional hazards (PH) assumption; a non-zero slope is evidence of departure from PH. The PH assumption will be formally tested using Schoenfeld's residual test (Schoenfeld, 1980^15 Therneau & Grambsch, 2000^17). Large departures from PH will be evidenced by a p-value <0.05.

If these show large departures from proportional hazards, then EFS based on central pathology assessment of biopsies and independent review of imaging scans will also be analyzed based on restricted mean survival time (RMST) differences (Zhang, 2013).

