### **Restricted Mean Survival Time (RMST)**

The hazard ratio estimate from the Cox's PH model is routinely used to empirically quantify the between-arm difference under the assumption that the ratio of the two hazard functions is constant over time. When this assumption is plausible, such a ratio estimate may capture the relative difference between two survival curves. However, the clinical meaning of such a ratio estimate is difficult, if not impossible, to interpret when the underlying PH assumption is violated (i.e., the hazard ratio is not constant over time).

The RMST is a robust and clinically interpretable summary measure of the survival time distribution and is equivalent to the area under the Kaplan-Meier curve from 'start date' through a specific cut-off point. Unlike median survival time, it is estimable even under heavy censoring. There is a considerable body of methodological research (e.g., Royston and Parmar, 2011, Uno, Wei, et al., 2014; Zhang, 2013) about the use of RMST to estimate treatment effects as an alternative to the hazard ratio approach.

The RMST methodology is applicable independently of the PH assumption and can be used, at a minimum, as a sensitivity analysis to explore the robustness of the primary analysis results. However, when large departures from the PH assumption are observed, the log-rank test is underpowered to detect differences between the survival distributions for the treatment arms, and a test of the difference between the RMST for the experimental arm and the control arm may be more appropriate to determine superiority of the experimental arm compared to the control arm with respect to the time-to-event endpoint.

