In particular, as it pertains to the **cut-off point ( $\tau$ )** to evaluate the RMST, it is noted that the cut-off point should not exceed the minimum of the largest observed time for both treatment arms so that the RMST of all treatment arms being evaluated can be adequately estimated and comparison between treatments is feasible;  $\tau$  should be clinically meaningful and closer to the end of the study follow-up so that the majority of survival outcomes will be covered by the time interval. The RMST up to time  $\tau$  can then be interpreted as the expected survival time restricted to the common follow-up time  $\tau$  among all participants. To avoid arbitrary selection of the common cut-off  $\tau$  for both treatment arms,  $\tau$  is pre-specified as:

$\tau$  = minimum of (largest observed EFS time for the experimental arm, largest observed EFS time for the control arm).

The treatment effect between the experimental arm and the control arm will be assessed based on the difference in RMST. The associated 95% CI for the difference in means and 1-sided p-value will be generated.

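### If the proportional hazards check fails, the SAP names centrally reviewed EFS for the RMST analysis, not the investigator-assessed EFS of the primary analysis

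*SAP*

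**What the plan says.** SAP Section 6.1.1.1 fixes the primary analysis: "The primary efficacy analysis will compare the EFS time based on the investigator assessment between Arm A and Arm C". Section 6.2.2.1 extends it to the other experimental arm: "The primary analysis of the key secondary endpoint of EFS for Arm B vs Arm C will repeat the primary analysis". Both use the investigator's assessment.

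Section 6.2.2.3 then opens with its purpose: "The following analyses will be performed to explore the robustness of the primary analysis results". Under its heading on model assumptions it checks proportional hazards by plots and by a Schoenfeld residual test, and takes p<0.05 as evidence of a large departure. The consequence of a large departure is that "EFS based on central pathology assessment of biopsies and independent review of imaging scans will also be analyzed", using RMST differences. No other version of EFS is named there.

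The RMST text that follows is general. It says the method "can be used, at a minimum, as a sensitivity analysis to explore the robustness of the primary analysis results". It sets the truncation time from the largest observed EFS times in the two arms, and then says: "The treatment effect between the experimental arm and the control arm will be assessed based on the difference in RMST", with a 95% CI and a 1-sided p-value. It names no assessor.

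Centrally reviewed EFS has its own place in the plan. Section 6.2.2 says that "EFS by BICR assessment will be analyzed as a secondary endpoint", and it is also the first sensitivity analysis listed in Section 6.2.2.3.

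In the protocol, Section 9.4.1.1 attaches an RMST footnote to the Cox analysis in the investigator-assessed EFS row. The footnote says that RMST can be used when proportional hazards fails badly. It does not say that it will be.

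**The concern.** When hazards are not proportional, the SAP's own reasoning is that the hazard ratio loses its clear clinical meaning and that RMST gives an interpretable substitute. The hazard ratio that most needs a substitute is the one reported for the primary comparison and for the key secondary EFS comparison, and both are investigator-assessed. The sentence that triggers RMST points to a different event set.

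Read literally, a failed check would give a committed between-arm alternative for centrally reviewed EFS. Nothing equally firm would exist for the endpoint whose model assumption was in doubt. Kaplan-Meier medians and rates for investigator-assessed EFS would still be reported, but they describe each arm separately and are not a between-arm measure.

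**Working it through.** No arithmetic applies: the point depends on no event count, power or alpha. The check is to set the statements side by side.

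| Place | Which EFS | Strength of wording |
|---|---|---|
| SAP 6.1.1.1, primary analysis, A vs C | Investigator | Fixed |
| SAP 6.2.2.1, key secondary, B vs C | Investigator | Fixed, repeats 6.1.1.1 |
| SAP 6.2.2.3, purpose | Robustness of the primary analysis | Fixed |
| SAP 6.2.2.3, RMST trigger sentence | Central pathology and imaging review | Committed |
| SAP 6.2.2.3, RMST text, use of method | Primary analysis results | Permissive |
| SAP 6.2.2.3, RMST text, truncation time and effect measure | EFS, assessor not named | Committed, object unclear |
| Protocol 9.4.1.1, RMST footnote | Investigator row | Permissive |

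1. **Which EFS is being checked?** The model-assumptions text does not name an assessor. That it is the investigator version is an inference from the section's stated purpose and from the stratified Cox model in Section 6.1.1.1.

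2. **Which EFS is named for RMST?** Only the centrally reviewed version. The SAP's other uses of RMST concern OS (by cross-reference in Section 6.2.2.4) and duration of complete response (Section 6.2.2.6). Neither is a version of EFS.

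3. **Is the named version the same as EFS per BICR?** Probably. The SAP Introduction describes BICR as covering pathology, imaging and oncology review, while the trigger sentence mentions only the first two. I take it to mean EFS per BICR, and the wording should be brought into line.

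4. **Can the sentence be read as covering EFS in general?** Not safely. In the main list of sensitivity analyses in Section 6.2.2.3, apart from the two COVID-19 items, each entry says whether it uses investigator assessment or BICR results. The informative-censoring analysis also names the investigator. A sentence in that section that specifies central review should be taken at its word.

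5. **What is left uncommitted?** One between-arm RMST table for each of two comparisons, so 2 × 1 = 2 tables, conditional on the check failing.

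**The case against.** The best defence is that the RMST text already covers the primary endpoint. It speaks of the robustness of the primary results, as the section's opening does. It says the effect will be assessed by the RMST difference, and it defines the truncation time on EFS time, the same term that Section 6.1.1.1 uses for investigator assessment. The SAP usually marks BICR when it means BICR. Section 2.1, which lists departures from the protocol's analysis plan, does not mention RMST, so the protocol footnote is not shown to be withdrawn.

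Much of this stands. RMST on investigator-assessed EFS is not excluded, and a reader might go too far by inferring that the SAP drops or forbids it. But the firm wording in the RMST text follows directly from a sentence whose only named object is centrally reviewed EFS, and the wording that mentions the primary results is permissive. That leaves the commitment unclear.

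Three further inferences are tempting and not supported.

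- **That RMST could replace the log-rank test.** The SAP does say that an RMST test "may be more appropriate to determine superiority of the experimental arm compared to the control arm". This is methodological background in a robustness section. SAP Sections 5.1.1 and 6.1.1.1 and Protocol Section 9.4.1.1 all fix the log-rank test for EFS, stratified in the analysis sections, and SAP Section 6.2.2.2 does the same for OS.
- **That OS has the same fault.** Section 6.2.2.4 carries the methods over to OS, where there is no assessor to confuse, and describes the OS sensitivity analyses as purely exploratory.
- **That the event set would be chosen after seeing results by arm.** SAP Section 7.1 says when the study team sees summaries by arm. It does not say that this choice is deferred until then.

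**Conclusion.** The concern holds as a wording error with a narrow consequence. The SAP's stated rule for a failed proportional hazards check names a secondary version of EFS, in a section meant to test the investigator-assessed primary analysis. Other text in both documents permits the intended analysis without clearly committing to it.

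Severity is low. What is affected is a supportive, conditional table for each of two comparisons. H01 and H02 are decided by the log-rank test, and alpha, event numbers and power are untouched. How often the check would fail depends on treatment-effect patterns that the documents do not give, so no frequency is attached to the point.

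The conclusion rests on two inferences: that the model being checked is the investigator-assessed one, and that the centrally reviewed version named is EFS per BICR. If the second were wrong, the sentence would name a version of EFS that the SAP defines nowhere else, and the case for correcting it would be stronger.

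**What to change.** Replace the object of the trigger sentence in SAP Section 6.2.2.3. Suggested wording: *If large departures from proportional hazards are found, RMST differences will be estimated for investigator-assessed EFS (Arm A vs Arm C and Arm B vs Arm C, FAS, Table 11 censoring), and the same will be done for EFS per BICR.*

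Optionally, add one sentence at the end of the RMST text: *The RMST p-value is supportive; the stratified log-rank test remains the confirmatory test.* This removes any doubt raised by the background remark on superiority, although the confirmatory test is already fixed elsewhere.

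No edit is needed for OS. The cost is one or two sentences in the SAP and, only if the check fails, one additional table per comparison.
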